| Section 8.2.4 Electrocardiograms | Clarification that ECG readings can be stored as physical copies in subject's source files. | Clarification | Non-substantial |

| Section # and Name | Description of Change | Brief Rationale | Substantial/ Non-substantial |
|--|--|--|---------------------------------|
| Section 8.4.6 Medical device deficiencies; Section 8.4.6.1 Time period for detecting medical device deficiencies; Section 8.4.6.2 Follow-up of medical device deficiencies; Section 8.4.6.3 Prompt reporting of medical device deficiencies to Sponsor; Section 8.4.6.4 Regulatory reporting requirements for device deficiencies; Appendix G Medical device AEs, ADEs, SAEs, SADEs, USADEs and medical device deficiencies: definitions and procedures for recording, evaluating, follow-up, and reporting in medical device studies | New sections added to discuss device constituent deficiencies. | New sections to discuss device deficiencies in line with new EU/US regulations and CSP template. | Substantial |

Version 4.0, 01 July 2020

In this amendment to the protocol:

- Section 4.1.1 (Study conduct mitigation during study disruptions due to cases of civil crisis, natural disaster, or public health crisis), Section 8 (Study assessments and procedures), Section 9.7 (Sensitivity analyses), and Appendix B:
 - New text was added to clarify how the study could continue in the event of a serious disruption, including details of mitigations that could be employed to ensure study continuity.
- Section 5.1 (Inclusion criteria):
 - The duration of mandatory contraception use during the study was updated: contraception to be used for 12 weeks (rather than 4 months) after the last dose of IP.

- Section 6.3.3 (After investigational product administration) and Section 8.4.4 (Management of investigational product-related reaction):
 - The minimum observation time (for the appearance of acute drug reactions) following investigational product administration was shortened to 1 hour.
- Section 6.6 (Concomitant therapy):
 - The study period during which the use of live attenuated vaccines was prohibited was updated: live attenuated vaccines use prohibited for 12 weeks (rather than 4 months) after the last dose of IP.
- Section 7.1 (Discontinuation of study treatment):
 - Criteria for discontinuation due to missed doses of IP updated to specify applicable to Part A only.
- Section 8.1.1.2 (Spirometry technique)
 - The procedure for performing a forced expiratory manoeuvre in children aged <10 years was clarified.
- Section 8.2.1 (Clinical safety laboratory assessments [Table 8]):
 - Procedures hepatitis B surface antigen screening updated.
- Section 8.4.3 (Overdose):
 - Section updated to specify dose considered as an overdose.
- Title page:
 - Sponsor details updated to include AstraZeneca Japan.
- Minor editorial changes throughout the document to clarify text, improve consistency, and to align the language and terminology used in the latest Clinical Study Protocol template.

Version 3.0, 22 August 2019

In this amendment to the protocol, the requirement that patients aged 12 to 14 years must weigh at least 35 kg has been removed. This change has been applied to the Synopsis and to Sections 4.1, 5.1, 6.1, 6.1.1 (Table 3) and 9.5.2. The rationale for this change has been added to Section 4.3.

Text to describe the cohort of Japanese patients aged 12 to 14 years has been added to the Synopsis and to Sections 4.1 and 9.2.

Minor changes have been made throughout to clarify text and improve consistency.

Version 2.0, 22 July 2019

In this amendment to the protocol:

Table 1:

- The window for the screening visit has been updated.
- Windows for Visit 3, Visit 4, and Visit 5 have been updated to be consistent with the window for the PK sample at these visits.
- Interviewer-administered Asthma Control Questionnaire (ACQ-IA) has been added at Visit 2, Visit 4, Visit 5, Visit 11, Visit 12, and Visit 14.
- Interviewer-administered Patient Global Impression of Change (PGIC-IA) has been added at Visit 9, Visit 10, Visit 11, Visit 13 and at the early discontinuation (DXD)/early withdrawal (WD) visit.
- Clinician Global Impression of Change (CGIC) has been added at Visit 9, Visit 10, Visit 11, Visit 13 and at the DXD/WD visit.
- Forced expiratory volume in 1 second (FEV₁) has been added at Visit 2.
- Urinalysis has been added at screening and at Visit 6, Visit 7, Visit 8, Visit 9, Visit 10, Visit 13, and at the DXD visit, to be consistent with the text of Section 8.2.1.
- Asthma exacerbation has been added to all visits except Visit 1 and Visit 2.
- Pregnancy test, pharmacokinetic (PK) sampling and anti-drug antibody (ADA) sampling assessments have been updated with a corresponding footnote added to indicate when these assessments should be performed pre-dose.
- The schedule of ADA sampling has been updated
- Sampling for neutralizing antibodies (nAb) has been deleted from the ADA sampling row, and from the table footnotes.
- The table has been reorganised to follow the recommended sequence for the completion of assessments at each visit.

Synopsis

- PPD has been added as the international co-ordinating investigator.

Synopsis and Section 2.2, Section 4.1, Section 4.2, Section 5.1, and Section 9.5.2

- Inclusion of patients aged 12 to 14 years and weighing at least 35 kg in Japan has been added.

Synopsis and Section 3:

- Presence of neutralizing antibodies has been deleted from the secondary objectives.
- ACQ-IA has been added at Weeks 1, 2, 32, and 40 and at the follow-up visit in the secondary endpoints.
- PGIC-IA has been added at Week 16 (Part A), and Weeks 24, 32 and 48 (Part B) and at the DXD/WD visit.
- CGIC has been added at Week 16 (Part A), and Weeks 24, 32 and 48 (Part B) and at the DXD/WD visit.
- Annualized asthma exacerbation rate (AAER) has been added as an exploratory objective.

Synopsis and Section 4.1, Section 6.1, Section 6.1.1, and Section 9.5.2:

- Stratification by body weight <40 kg / ≥40 kg has been changed to stratification by body weight <35 kg / ≥35 kg.
- The dose of ~~CCI~~ mg to be administered to patients in the lower weight stratum (previously <40 kg) has been changed to ~~CCI~~ mg for the updated lower weight stratum of <35 kg.

Synopsis and Section 4.1:

- A statement has been added to allow the screening period to be extended if necessary.
- The statement that any of the first 4 patients in each cohort will be replaced if the patient misses a dose or a scheduled assessment has been deleted.

Section 2.3:

- A statement has been added concerning the risk related to hypersensitivity reactions.

Section 4.1:

- A statement has been added to clarify the requirements for patients in Part A to be evaluable, and that non-evaluable patients in Part A will be replaced.

Section 4.3:

- The justification for the dose of benralizumab has been updated to provide a rationale for the use of ~~CCI~~ mg in patients weighing <35 kg.

Section 5.1:

- The Japanese Pediatric Asthma Guidelines have been added to inclusion criterion 3.
- Definition of inhaled corticosteroid relevant to Japan has been added to inclusion criterion 6.

Section 6.1.2:

- Section 6.1.2 Medical Devices has been deleted, as it is not applicable to this study.

Section 6.2

- Further information has been added relating to storage of the investigational product (IP) and to actions to be taken in case of temperature excursions or damage to the IP or IP packaging.

Section 6.6:

- 'Five-lipoxygenase inhibitors' has been deleted from the table of prohibited medications.

Section 8:

- A recommended sequence for the completion of assessments at each visit has been added.
- Table 7 has been updated to include detail of the type of samples to be taken at each visit in addition to the volume of blood to be taken at each visit.

Section 8.1.2:

- A rationale has been added for the completion of the ACQ-IA at all visits during the treatment and post-treatment periods.

- A description of the PGIC-IA has been added.
- A description of the CGIC has been added.

Section 8.2.1, Section 8.3.8, Section 11 (Appendix D):

- References to liver enzyme elevations and to Hy's Law have been deleted.

Section 8.2.5.3:

- Reference to patients older than 9 years of age has been deleted.

Section 8.2.5.5:

- A section describing asthma exacerbation has been added.

Section 8.4.6:

- Section 8.4.6 Medical Device Malfunctions has been deleted, as it is not applicable to this study.

Section 8.5.1:

- Further detail has been added concerning the time and date of blood sampling for PK analysis.

Section 8.10.1:

- Testing for neutralizing antibodies has been deleted.

Section 8.10.2:

- Reference to neutralizing antibodies has been deleted.

Section 9.3

- The definition of patient evaluability has been updated.

Section 9.5.4.4

- PGIC-IA and CGIC have been added.

Section 9.5.6

- A description of the analysis of asthma exacerbation has been added.

Section 9.6.2:

- Reference to the SRC charter has been added, and detail of possible SRC recommendations has been deleted.

Throughout:

- Minor changes have been made to clarify text and improve consistency.

Version 1.0, 22 June 2018

Initial creation

This Clinical Study Protocol has been subject to a peer review according to AstraZeneca Standard procedures. The Clinical Study Protocol is publicly registered and the results are disclosed and/or published according to the AstraZeneca Global Policy on Bioethics and in compliance with prevailing laws and regulations.

TABLE OF CONTENTS

| | |
|---|----|
| TITLE PAGE..... | 1 |
| PROTOCOL AMENDMENT SUMMARY OF CHANGES TABLE..... | 2 |
| TABLE OF CONTENTS | 9 |
| 1 PROTOCOL SUMMARY | 13 |
| 1.1 Schedule of Activities (SoA) | 13 |
| 1.2 Synopsis..... | 16 |

1 PROTOCOL SUMMARY

1.1 Schedule of Activities (SoA)

Table 1 Schedule of assessments

| | Part A – PK, PD, Safety | | | | | | | | | | Part B- Safety | | | | DXD/ WD | For details see Section |
|---------------------------------|------------------------------------|----------|----------------|----------------|----------------|----------------|----------------|----------------|----------------|------------|------------------|------------------|------------------------|------------------------|------------|----------------------------------|
| | 1 SCRN Days -28 to -14 | 2 | 3 +1 day | 4 ±3 day | 5 ±4 day | 6 ±7 day | 7 ±7 day | 8 ±7 day | 9 ±7 day | 10 | 11 ±7 days | 12 ±7 days | 13 EOT ±7 day | 14 F/U ±7 day | | |
| Visit | | | | | | | | | | | | | | | | |
| Visit windows | | | | | | | | | | | | | | | | |
| Week | - | 0 | 0 | 1 | 2 | 4 | 8 | 12 | 16 | 24 | 32 | 40 | 48 | 52 | - | Section |
| Day | - | 0 | 1 | 7 | 14 | 28 | 56 | 84 | 112 | 168 | 224 | 280 | 336 | 362 | - | - |
| Written informed consent/assent | X | | | | | | | | | | | | | | | Appendix A 3 |
| Inclusion/exclusion criteria | X | X | | | | | | | | | | | | | | 5.1, 5.2 |
| ACQ-IA | X | X | | X | X | X | X | X | X | X | X | X | X | X | | 8.1.2 |
| PGIC-IA | | | | | | | | | X | X | X | | X | | | 8.1.2 |
| CGIC | | | | | | | | | X | X | X | | X | | | 8.1.2 |
| Body weight and height | X | | | | | | | | X | X | | | X | | | 8.2.5.1 |
| Patient stratification | X | | | | | | | | | | | | | | | 6.1 |
| Vital signs | X | X | X | X | X | X | X | X | X | X | X | X | X | X | | 8.2.3 |
| Medical/surgical history | X | X | | | | | | | | | | | | | | 8.2.5.2 |
| 12-lead ECG | X | | | | | | | | X | | | | X | | | 8.2.4 |

Table 1 Schedule of assessments

| | Part A – PK, PD, Safety | | | | | | | | | | Part B- Safety | | | | | DXD/ WD | For details see Section |
|--|------------------------------------|----------------|-----------|-----------|-----------|----------------|----------------|-----------|----------------|----------------|----------------|----------------|-------------------------|------------------------|---|-----------------|----------------------------------|
| | 1 SCRN Days -28 to -14 | 2 | 3 | 4 | 5 | 6 | 7 | 8 | 9 | 10 | 11 | 12 | 13 EOT ±7 days | 14 F/U ±7 day | | | |
| Visit | | | | | | | | | | | | | | | | | |
| Visit windows | | | +1 day | ±3 day | ±4 day | ±7 day | ±7 day | ±7 day | ±7 day | ±7 day | ±7 days | ±7 days | ±7 day | ±7 day | | | |
| Week | - | 0 | 0 | 1 | 2 | 4 | 8 | 12 | 16 | 24 | 32 | 40 | 48 | 52 | - | Section | |
| Day | - | 0 | 1 | 7 | 14 | 28 | 56 | 84 | 112 | 168 | 224 | 280 | 336 | 362 | - | - | |
| Complete PE (pre-dose) | X | X | | | | | | | X | | | | X | | X | 8.2.2 | |
| Brief PE (pre- dose) | | | | | | X | X | X | | X | X | X | | | | 8.2.2 | |
| FEV ₁ | X | X | | | | X | X | X | X | X | | | X | | X | 8.1.1 | |
| Clinical chemistry assessments | X ^a | a | | | | X | X | X | X | | | | X | | X | 8.2.1 | |
| Haematology (CBC + differential) | X ^a | a | | | | X | X | X | X | | | | X | | X | 8.2.1, 8.6.1 | |
| Serology (hepatitis B, C, HIV) | X | | | | | | | | | | | | | | | 8.2.1 | |
| Urinalysis | X | | | | | X | X | X | X | X | | | X | | X | 8.2.1 | |
| Pregnancy test | X | X ^b | | | | X ^b | X ^b | X | X ^b | X ^b | X ^b | X ^b | X | | X | 8.2.5.3 | |
| Concomitant medications | X | X | X | X | X | X | X | X | X | X | X | X | X | X | X | 8.2.5.4 | |
| Asthma exacerbation | | | X | X | X | X | X | X | X | X | X | X | X | X | X | 8.2.5.5 | |
| Adverse events | X | X | X | X | X | X | X | X | X | X | X | X | X | X | X | 8.3 | |
| PK sampling | | X ^b | X | X | X | X ^b | X ^b | X | X ^b | X ^b | | | X | | X | 8.5 | |

Table 1 Schedule of assessments

| Visit | Part A – PK, PD, Safety | | | | | | | | | | Part B- Safety | | | | | DXD/ WD | For details see Section |
|---------------------------|------------------------------------|----------------|-----------|-----------|-----------|----------------|-----------|----------------|----------------|------------|----------------|------------|------------|------------|---|------------|----------------------------------|
| | 1 SCRN Days -28 to -14 | 2 | 3 | 4 | 5 | 6 | 7 | 8 | 9 | 10 | 11 | 12 | 13 EOT | 14 F/U | | | |
| Visit windows | +1 day | ±3 day | ±4 day | ±7 day | ±7 day | ±7 day | ±7 day | ±7 day | ±7 day | ±7 days | ±7 days | ±7 days | ±7 day | ±7 day | - | Section | |
| Week | - | 0 | 0 | 1 | 2 | 4 | 8 | 12 | 16 | 24 | 32 | 40 | 48 | 52 | - | | |
| Day | - | 0 | 1 | 7 | 14 | 28 | 56 | 84 | 112 | 168 | 224 | 280 | 336 | 362 | - | - | |
| ADA sampling | | X ^b | | | | X ^b | | X ^b | X ^b | | | X | | X | | 8.10 | |
| Single-dose IP injections | | X | | | | X | X | | X | X | X | X | | | | 6.1 | |

^a The screening clinical chemistry/haematology samples at Visit 1 (Day -28 to Day -14) will constitute baseline values provided that Visit 2 (Day 0) is done ≤ 28 days after Visit 1. If so, no safety laboratory samples will need to be collected at Visit 2.

^b To be performed before IP is administered at these visits.

Abbreviations: ACQ-IA interviewer-administered asthma control questionnaire, ADA anti-drug antibody(ies), CBC complete blood count, CGIC clinician global impression of change, DXD early discontinuation, ECG electrocardiogram, exam examination, EOT end of treatment, FEV₁ forced expiratory volume in 1 second, F/U follow-up, HIV human immunodeficiency virus, IP investigational product, PD pharmacodynamics, PE physical examination, PGIC-IA interviewer administered patient global impression of change, PK pharmacokinetics, SCRN screening, std standard, WD early withdrawal.

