3 OBJECTIVES AND ENDPOINTS

Study objectives and endpoints are shown in [Table 2](#).

Table 2 **Study objectives and endpoints**

| Primary objectives: | Endpoints/variables: |
|--|--|
| To evaluate the pharmacokinetics (PK) of benralizumab administered subcutaneously (SC) in children from 6 to 11 years of age with severe eosinophilic asthma | 
 ● Clearance ● Area under concentration time curve to Day 28 (AUC₀₋₂₈) ● Maximum serum concentration (C_{max}) ● Terminal phase elimination half-life (t_{1/2}) ● Time to reach C_{max} (T_{max}) |
| To evaluate the pharmacodynamics (PD) of benralizumab administered SC in children from 6 to 11 years of age with severe eosinophilic asthma | Change from baseline in peripheral blood eosinophil count at Weeks 4, 8, 12 and 16 (Part A), and Weeks 24 and 48 (Part B) |
| Secondary objectives: | Endpoints/variables: |
| To characterize the PK of benralizumab | Body weight-adjusted clearance |
| To evaluate the immunogenicity of benralizumab | Presence of anti-benralizumab antibodies |
| To evaluate the effect of benralizumab on pulmonary function | Change from baseline in pre-dose (when applicable), pre-bronchodilator, FEV ₁ measured at Weeks 4, 8, 12, and 16 (Part A), and Weeks 24 and 48 (Part B) |
| To assess the effect of benralizumab on asthma symptoms and other asthma control metrics | Change from baseline in ACQ-IA score, measured at screening and Weeks 1, 2, 4, 8, 12, and 16 (Part A), and Weeks 24, 32, 40 and 48, and at follow-up (Part B) PGIC-IA, measured at Week 16 (Part A), Weeks 24, 32 and 48 (Part B), and at the DXD/WD visit CGIC, measured at Week 16 (Part A), Weeks 24, 32 and 48 (Part B), and at the DXD/WD visit |
| Safety objective: | Endpoints/variables: |
| To assess the safety and tolerability of benralizumab | AEs Vital signs Collection of clinical chemistry/haematology parameters and urinalysis |
| Exploratory objective: | Endpoints/variables: |
| To evaluate exacerbations experienced | Annualized asthma exacerbation rate (AAER) |

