8 STUDY ASSESSMENTS AND PROCEDURES

Study procedures and their timing are summarised in [Table 1](#).

The investigator will ensure that data are recorded in the eCRF. The Web Based Data Capture system will be used for data collection and query handling.

The investigator ensures the accuracy, completeness, legibility, and timeliness of the data recorded in the eCRF and of the provision of answers to data queries according to the Clinical Study Agreement. The investigator will sign the completed eCRF. A copy of the completed eCRF will be archived at the study site. Additional data to assess the impact of civil crisis, natural disaster, or public health crisis will be collected.

Immediate safety concerns should be discussed with the sponsor immediately upon occurrence or awareness to determine if the patient should continue or discontinue study treatment.

Adherence to the study design requirements, including those specified in [Table 1](#), is essential and required for study conduct.

All screening evaluations must be completed and reviewed to confirm that potential patients meet all eligibility criteria. The investigator will maintain a screening log to record details of

all patients screened and to confirm eligibility or record reasons for screening failure, as applicable.

Procedures conducted as part of the patient's routine clinical management and obtained before signing of the ICF may be utilised for screening or baseline purposes provided the procedures met the protocol-specified criteria and were performed within the time frame defined in [Table 1](#).

The recommended sequence for completion of assessments at each visit is:

- Complete ACQ-IA, PGIC-IA, CGIC
- Measure vital signs, ECG, conduct physical examination
- Conduct spirometry assessment
- Take blood samples
- Administer benralizumab.

Based on the European Medicines Agency's (EMA) Ethical Considerations for Clinical Trials on Medicinal Products Conducted with the Paediatric Population ([EMA 2008](#)), the maximum amount of blood collected, including any losses in the manoeuvre, from each patient should not exceed 3% of the total blood volume during a period of 4 weeks and should not exceed 1% at any single time during the study (Table 6).

Table 6 Maximum volume of blood to be withdrawn from a patient

| Patient weight (kg) | Total blood volume (mL) ^a | Maximum blood volume (mL) to be withdrawn at any visit | Maximum blood volume (mL) to be withdrawn within a 4-week period |

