|---------------------|--------------------------------------|--|--|
| 15-20 | 1200-1600 | 12.0-16.0 | 36.0-48.0 |
| 21-25 | 1680-2000 | 16.8-20.0 | 50.4-60.0 |
| 26-30 | 2080-2400 | 20.8-24.0 | 62.4-72.0 |
| 31-35 | 2480-2800 | 24.8-28.0 | 74.4-84.0 |
| 36-40 | 2880-3200 | 28.8-32.0 | 86.4-96.0 |
| 41-45 | 3280-3600 | 32.8-36.0 | 98.4-108.0 |
| 46-50 | 3680-4000 | 36.8-40.0 | 110.8-120.0 |
| 51-55 | 4080-4400 | 40.8-44.0 | 122.4-132.0 |
| 56-60 | 4480-4800 | 44.8-48.0 | 134.4-144.0 |
| 61-65 | 4880-5200 | 48.8-52.0 | 146.4-156.0 |
| 66-70 | 5280-5600 | 52.8-56.0 | 158.4-168.0 |
| 71-75 | 5680-6000 | 56.8-60.0 | 170.4-180.0 |
| 76-80 | 6080-6400 | 60.8-64.0 | 182.4-192.0 |

Table 6 Maximum volume of blood to be withdrawn from a patient

| Patient weight (kg) | Total blood volume (mL) ^a | Maximum blood volume (mL) to be withdrawn at any visit | Maximum blood volume (mL) to be withdrawn within a 4-week period |
|---------------------|--------------------------------------|--|--|
| 81-85 | 6480-6800 | 64.8-68.0 | 194.4-204.0 |
| 86-90 | 6880-7200 | 68.8-72.0 | 206.4-216.0 |
| 91-95 | 7280-7600 | 72.8-76.0 | 218.4-228.0 |
| 96-100 | 7680-8000 | 76.8-80.0 | 230.4-240.0 |

^a The total blood volume is estimated at 80 mL/kg body weight.

Source: [EMA 2008](#)

The total maximum volume of blood that will be withdrawn from each patient at each study visit is listed in Table 7.

Table 7 Maximum volume of blood to be withdrawn from each patient

| Visit | Samples required | Total maximum volume (mL) ^a |
|-----------------------------|---|--|
| Visit 1 (Screening) | clinical chemistry; haematology; serology | 13.0 |
| Visit 2 | PK; ADA | 5.0 |
| Visit 3 | PK | 2.5 |
| Visit 4 | PK | 2.5 |
| Visit 5 | PK | 2.5 |
| Visit 6 | clinical chemistry; haematology; PK | 7.0 |
| Visit 7 | clinical chemistry; haematology; PK; ADA | 9.5 |
| Visit 8 | clinical chemistry; haematology; PK | 7.0 |
| Visit 9 | clinical chemistry; haematology; PK; ADA | 9.5 |
| Visit 10 | clinical chemistry; haematology; PK; ADA | 9.5 |
| Visit 11 | | 0 |
| Visit 12 | | 0 |
| Visit 13 (End of Treatment) | clinical chemistry; haematology; PK; ADA | 9.5 |
| Visit 14 (Follow-up) | | 0 |
| Early discontinuation (DXD) | clinical chemistry; haematology; PK; ADA | 9.5 |
| Total (mL) | | 87.0 |

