8.2.1 Clinical safety laboratory assessments

See Table 8 for the list of clinical safety laboratory tests to be performed and Table 1 for the timing and frequency. All protocol-required laboratory assessments, as defined in Table 8, must be conducted in accordance with the laboratory manual and Table 1.

The investigator should assess the available results with regard to clinically relevant abnormalities. The laboratory results should be signed and dated and retained at the centre as source data for laboratory variables.

For information on how AEs based on laboratory tests should be recorded in the eCRF and reported, see Section [8.3.7](#).

Local clinical routine procedures to reduce pain and discomfort from blood sampling in children will be followed, eg, offering topical anaesthesia, coordinated sampling to avoid repeated punctures and use of in-dwelling catheters as appropriate in accordance with ethical and instruction guidelines for paediatric blood sampling. Additional safety samples may be collected if clinically indicated at the discretion of the investigator.

The clinical chemistry, haematology, virology, and urinalysis will be performed at a central laboratory.

Table 8 Laboratory safety variables

| Haematology (complete blood counts with differential) | Clinical chemistry (serum or plasma) |
|--|---|
| B-Haemoglobin (Hb) | S/P-Creatinine |
| B-basophil count differential count (absolute count) | S/P-Bilirubin, total |
| B-lymphocyte differential count (absolute count) | S/P-Alkaline phosphatase (ALP) |
| B-Platelet count | S/P-Aspartate transaminase (AST) |
| B-eosinophil count differential count (absolute count) | S/P-Alanine transaminase (ALT) |
| B-monocytes differential count (absolute count) | S/P-Glucose |
| B-neutrophils differential count (absolute count) | S/P-C-reactive protein |
| White blood cell (WBC) count | S/P-Urea |
| | S/P-Albumin |
| Urinalysis (dipstick) | S/P-Potassium |
| U-Hb/Erythrocytes/Blood | S/P-Calcium, total |
| U-Protein/Albumin | S/P-Sodium |
| U-Glucose | S/P-Creatine kinase (CK) |
| | S-hCG test (Section 8.2.5.3) |
| Virology screen | |
| Hepatitis B surface antigen (HBsAG) ^a | |
| Hepatitis C virus (HCV) | |
| Human immunodeficiency virus (HIV) | |

^a If a positive antibody test from Hepatitis B surface antigen (HBsAG) is received, standard reflex confirmation testing is to be carried out.

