8.6 Pharmacodynamics

8.6.1 Collection of samples

Samples for analysis of peripheral blood eosinophils will be collected as part of standard haematology assessment (complete blood count [CBC], [Section 8.2.1](#)) at timelines as specified in [Table 1](#). Sampling will occur pre-dose on visits when IP is administered.

Samples will be collected, labelled, stored, and shipped as detailed in the Laboratory Manual.

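### Protocol Table 1 schedules no haematology at Visit 10 (Week 24), although the Week 24 eosinophil change is a named primary PD time point

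*Protocol*

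**What the plan says.** Protocol Section 3 (Table 2) defines the primary PD endpoint as "Change from baseline in peripheral blood eosinophil count at Weeks 4, 8, 12 and 16 (Part A), and Weeks 24 and 48 (Part B"). The Synopsis and SAP Sections 1.1.1 and 3.2.2.1 name the same weeks.

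There is no separate PD tube. Protocol Section 8.6.1 states: "Samples for analysis of peripheral blood eosinophils will be collected as part of standard haematology assessment", and it refers to Table 1 for the timing. Section 8.2.1 says that the laboratory assessments "must be conducted in accordance with the laboratory manual and Table 1". Section 8 makes compliance with Table 1 mandatory in the sentence that begins "Adherence to the study design requirements, including those specified in". SAP Section 3.2.2.1 also takes the eosinophil sampling times from Protocol Table 1.

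In Table 1, the "Haematology (CBC + differential" row is marked at Visits 1, 6, 7, 8, 9, 13 and DXD/WD, with only footnote a at Visit 2. The Visit 10 cell is empty. The clinical chemistry row is identical.

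Two other places assume that the sample exists. Protocol Table 7 has the line "Visit 10 | clinical chemistry; haematology; PK; ADA | 9.5", and its footnote counts Visit 10 among the visits whose samples can serve a serum pregnancy test. SAP Table 1 gives chemistry and haematology a Week 24 window of Days 140 to 251.

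**The concern.** The only table that tells a site when to draw haematology leaves out a visit at which a primary endpoint is defined. If sites follow it, the Week 24 eosinophil change is missing by design, and the Part B pharmacodynamic evidence rests on Week 48 alone. Week 24 safety chemistry would be missing too.

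Collection could also be uneven. Some sites may work from Table 1 and others from Table 7. With about 30 children planned and as few as 8 in a weight stratum, a few absent values would change a by-visit summary noticeably. Under SAP Section 3.1.4, a patient with no value in a window is missing at that visit, but an unscheduled value inside the window is used. The Week 24 summary could therefore mix true Visit 10 samples with counts taken for other reasons on other days.

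**Working it through.** **1. Which column is Week 24.** The header row of Table 1 reads "Week | - | 0 | 0 | 1 | 2 | 4 | 8 | 12 | 16 | 24". The first entry is Visit 1, so 24 is the tenth entry: Visit 10, Day 168.

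**2. Marks in the same block of Table 1.** Each row has the same number of cells as the Week row.

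| Row | Visits marked | Visit 10 |
|---|---|---|
| FEV₁ | 1, 2, 6, 7, 8, 9, 10, 13, DXD/WD | yes |
| Clinical chemistry | 1, (2: footnote only), 6, 7, 8, 9, 13, DXD/WD | **no** |
| Haematology | 1, (2: footnote only), 6, 7, 8, 9, 13, DXD/WD | **no** |
| Urinalysis | 1, 6, 7, 8, 9, 10, 13, DXD/WD | yes |
| PK sampling | 2 to 10, 13, DXD/WD | yes |

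**3. Whether the columns in this block are aligned.**
- The urinalysis row matches the visits listed for urinalysis in the Version 2.0 amendment summary: screening, Visits 6 to 10, Visit 13 and DXD.
- The PK row matches the PK entries in Table 7 visit by visit.
- The FEV₁ row matches its endpoint weeks (4, 8, 12, 16, 24, 48).
- The haematology and chemistry marks on both sides of the gap (Visits 6 to 9, then 13 and DXD) match Table 7. A shifted row would also have displaced the later marks.

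**4. What Table 7 implies.** First, its stated total, summing Visits 1 to 14 and then DXD:

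13.0 + 5.0 + 2.5 + 2.5 + 2.5 + 7.0 + 9.5 + 7.0 + 9.5 + 9.5 + 0 + 0 + 9.5 + 0 + 9.5 = 87.0 mL, as printed.

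Component volumes:
- PK = 2.5 mL (Visit 3, PK alone).
- ADA = 5.0 − 2.5 = 2.5 mL, from "Visit 2 | PK; ADA | 5.0".
- Chemistry + haematology = 7.0 − 2.5 = 4.5 mL (Visit 6: chemistry, haematology and PK).

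Visit 10 with chemistry and haematology: 4.5 + 2.5 + 2.5 = 9.5 mL, as printed. Without them: 2.5 + 2.5 = 5.0 mL, and the total would be 87.0 − 4.5 = 82.5 mL. Table 7's figures hold only if the Week 24 sample is drawn.

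**5. Size of the gap.**
- Endpoint time points: 4, 8, 12, 16, 24 and 48, so 6 in all, 2 of them in Part B. Table 1 schedules 5, of which 1 is in Part B.
- Nominal interval without a scheduled count: 336 − 112 = 224 days. With Visit 10 restored, the first interval is 168 − 112 = 56 days.
- The SAP Week 24 window runs from 168 − 140 = 28 days before target to 251 − 168 = 83 days after it.

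**The case against.** The strongest objection is that the argument rests on an empty cell, and tables taken from a PDF can lose or shift marks. Parts of Table 1 do look damaged. The ADA row reads Visits 2, 6, 8, 9, 12 and 14, whereas Table 7 gives 2, 7, 9, 10, 13 and DXD. In the first segment the DXD/WD cells are blank even for PGIC-IA and CGIC, which the endpoints place at that visit. SAP Section 3.1.4 says that its windows follow the protocol's collection schedule, which suggests that its authors believed haematology was scheduled at Week 24. These faults lie in other segments of the table, however. The segment holding the laboratory rows passes the alignment checks above, and both laboratory rows would have had to lose the same single mark with nothing else moving.

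A second objection is that the sample is specified elsewhere: in Table 7, in the endpoint itself and perhaps in the laboratory manual, which is not available here. That stands in part. Loss of the sample is a risk, not a certainty. But Table 7 is a blood-volume table, and the text assigns timing to Table 1.

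A third is that the consequences are modest. No hypothesis is tested, PD is summarised descriptively, and five of the six time points are unaffected. The SAP selects the value closest to target and restricts DXD samples to one dosing cycle after the last dose, so an off-schedule count does not enter without any rule. All of this is true. It limits the damage but does not supply the missing value: where an unscheduled count is the only one in the window, closeness to target excludes nothing. The wide window comes from the SAP's general halfway rule and is not a separate error.

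**Conclusion.** The point holds. Protocol Table 1 omits the only sample that can provide the Week 24 value of the primary PD endpoint, and it conflicts with Table 2, Table 7 and SAP Table 1. A site following Table 1 loses 1 of 6 primary PD time points, 1 of 2 in Part B, with 224 days between scheduled counts. Week 24 chemistry is affected in the same way, although no objective names that week for chemistry, so its case rests on Table 7.

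This is an internal contradiction, not a deliberate design choice: the intention to sample is clear from Table 7. The conclusion assumes that the Visit 10 cells are blank in the approved protocol, which the internal checks support, and that the laboratory manual does not override Table 1. Because the omission affects a primary endpoint and costs almost nothing to correct, it should be corrected.

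**What to change.** Mark haematology and clinical chemistry at Visit 10 in Protocol Table 1, so that it agrees with Table 2, Table 7 and SAP Table 1. Visit 10 is a dosing visit, and Section 8.6.1 already requires the eosinophil sample before dosing. Footnote b could be added for clarity, but these rows do not carry it at the other dosing visits, so for consistency it would be needed there too. Check that the laboratory manual agrees.

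The cost is one line in the schedule. There is no new visit or extra venepuncture, because PK is already drawn at Visit 10. The 9.5 mL is already in Table 7 and is below the 12.0 mL single-visit limit that Table 6 gives for a 15 kg child.

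The Synopsis estimates last patient completed in September 2022 and the SAP was amended in October 2022, so sampling may already have finished. In that case the clinical study report should state, by weight group, how many Week 24 eosinophil values are true Visit 10 samples, how many are other counts falling in Days 140 to 251, and how many are missing.
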